3. OBJECTIVES

3.1 Primary Efficacy Objective

To evaluate change of IIEF-EF score⁹ from baseline to follow-ups 1, 3 and 6 months' post treatment (appendix I).

3.2 Secondary Objectives

To study sexual activity improvement leading to optimal penetration at follow-ups according to:

SEP- Sexual Encounter Profile: Questions 2 and 3 (appendix II)
GAQ- Global Assessment Questions (appendix III)
EHS- Erection Hardness Score (appendix IV)

4. STUDY DESIGN

4.1 Accrual goal

A total of 80 patients with Vasculogenic ED meeting the eligibility criteria will be recruited from the Department of Urology clinic.

4.2 Duration of Study Participation

The total duration of the study will be for 7 months— including 1-month pretreatment (washout) followed by a period of 6 months' follow-up after the treatment.

5. STUDY ENTRY AND ENROLLMENT AND WITHDRAWAL

5.1 Study Entry

Study entry, as used in this protocol, will be defined as a subject signing informed consent. Study enrollment, as used in this protocol, will be defined as the investigator's confirmation of the subject's eligibility by signing an eligibility checklist. As per University of Miami policy, each study participant, including participants who have screened failed, who signs an informed consent form should be entered into the study database.

5.2 Enrollment Procedure

Completed and signed protocol-specific eligibility checklist;
All pages of the original signed informed consent forms (ICFs), including HIPAA Form B;
Relevant source documents or medical records such as: subject medical history and physical exam, admission or discharge notes, diagnostic reports, pathologic confirmation of diagnosis, and relevant subject-specific written communication.
Documentation from the Investigator that he/she has determined the subject meets eligibility criteria.

5.3 Cancellation Guidelines

The following are reasons for withdrawal of subjects from the study:

- A subject does not meet the eligibility criteria; (the subject will be considered a screen failure).
- A subject withdraws consent,
- A subject die's during protocol participation from causes other than the study treatment (not due to adverse events) or
- A study investigator decides the subject should be withdrawn from the study (e.g. subject non-compliance)

Regardless of reason for withdrawal, once a patient has been randomized to an arm, an intention to treat analysis will be performed.

All subjects who either screen fails, is withdrawn from the study or has completed all visits should be de-enrolled from the research database within 48 hours.

6. PATIENT SELECTION/ELIGIBILITY CRITERIA

6.1 Inclusion (Eligibility) Criteria

- The patient must be able willing and able to provide informed consent.
- The patient is a male between ≥ 30 and ≤ 80 years of age.
- The patient has ED of Vasculogenic origin determined by penile duplex ultrasound.
- The patient is PDE5i responsive, meaning he is able to achieve and maintain an erection under the effect of the maximal dosage of PDE5i.
- The patient has been in a stable heterosexual relationship for over 3 months prior to enrollment.
- A minimum of 2 sexual attempts per month for at least one month prior to enrollment – as documented by the Sexual Health Questionnaire (SHIM).
- The patient is suffering from erectile dysfunction lasting for over 6 months and not more than 5 years as per history provided by patient.
- IIEF-EF score between 11 and 25.
- Testosterone level 300-1000 ng/dL within 1 month prior to enrollment.
- A1C level $\leq 7\%$ within 1 month prior to enrollment.
- Patients have at least a natural tumescence during sexual stimulation (EHS score ≥ 1).

6.2 Exclusion (Eligibility) Criteria

- The patient is currently or has participated in another study within the past three months, that may interfere with the results or conclusions of this study.
- The patient is under judicial protection (prison or custody).
- The patient is an adult under guardianship.
- The patient refuses to sign the consent.
- History of radical prostatectomy or extensive pelvic surgery ever.
- Venous leak.
- Past radiation therapy of the pelvic region within 12 months prior to enrollment.
- Recovering from any cancer within 12 months prior to enrollment.
- Neurological disease such as Alzheimers or Parkinsons disease which affects erectile function at the discretion of the investigator.

- Psychiatric diagnosis or medications such as antidepressants which affects erectile function or any other medications at the discretion of the investigator.
- Anatomical malformation of the penis, including Peyronie's disease.
- Testosterone level <300 or >1000 ng/dL within 1 month prior to enrollment.
- A1C level > 7% within 1 month prior to enrollment.
- The patient is taking blood thinners and has an international normalized ratio >3.

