1.2 Study Interventions

Renova-ED is a Linear Shockwaves (LISW) device which incorporates a unique shockwave transducer operable to deliver shockwaves to a treated region confined to a narrow rectangle. Shockwaves generation follows the electromagnetic principle.

Linear Shockwaves (LISW), as a treatment for ED has been in evaluation in contemporary medicine (see section 1.4). It has been in use for the last three years.

The present study is about a device called "Renova-ED", in which shockwaves are focused onto line segments for improved organ coverage. Shockwaves produced by "Renova-ED" are aimed at the left and right corpora cavernosa and the crura. The study is aimed at determining the safety and effectiveness of this new type LISW in the relief of ED.

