1.4 Preliminary Studies

Contemporary literature shows two important studies in this field both conducted by Vardi et al^{7,8}.

The efficacy trial study published in 2010 recruited 20 men with vasculogenic ED and were given serial 2 sessions of treatment for about 3 weeks followed by 3 – week no intervention period. At 1-month duration there was a significant improvement in their erectile function measured by International Index of Erectile Function ED (IIEF-ED) domain scores (20.9 5.8 vs 13.5 4.1, $p < 0.001$). This significant result was consistent at 6-month follow up. Moreover, no pain or adverse event was noted during the follow-up period.

The second randomized, double-blind, sham controlled study by showed that treatment group showed better outcome than control group measured using International Index of Erectile Function-Erectile Function domain (mean SEM 6.7 0.9 vs 3.0 1.4, $p 0.0322$) at the first follow-up. Additionally, penile hemodynamics improve significantly in the treatment group in comparison to control group (maximal post-ischemic penile blood flow 8.2 vs 0.1 ml per minute per dl, $p 0.0001$).

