7.3 Pre-Treatment Procedures and Evaluations

Upon evaluating the inclusion/exclusion criteria, patients will be recruited to the study and randomized into one of the two groups in a 1:1 ratio (randomization will be performed by a computer software maintained by the Department of Urology). Patients randomized to the treatment groups will be instructed to stop any use of PDE5i for 4 weeks prior to first treatment session and refrain from using any other ED therapy option during the study. They will be instructed to undergo a PDE5i washout period of 4 weeks prior to treatment and to avoid using PDE5i or any other ED treatment during the entire study duration (shockwave treatment and follow-ups). After the washout period and before the first treatment session, patients will answer the IIEF-EF, SEP and EHS questionnaires for baseline evaluation.

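### Men already given penile shockwave treatment in routine care are not excluded, so the baseline for the primary IIEF-EF change may carry an earlier effect

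*Combined protocol and SAP*

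**What the plan says.** Section 6.2 has one exclusion that touches earlier treatment: "The patient is currently or has participated in another study within the past three months". It is further limited to studies that could affect this trial's results. Neither section 6.1 nor section 6.2 mentions shockwave treatment. Section 6.2 does set look-back limits for other exposures: no time limit for radical prostatectomy or extensive pelvic surgery, and 12 months for pelvic radiation and for cancer.

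Section 7.3 controls treatment around baseline. "They will be instructed to undergo a PDE5i washout period of 4 weeks prior to treatment", it says, and it bars other ED therapy while the study runs. Neither provision reaches back to an earlier device treatment. Screening in section 7.2 collects medical and co-medication history and recent PDE5i use, without asking about earlier shockwave treatment.

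On exposure and duration of effect, section 1.2 says of linear shockwaves for ED: "It has been in use for the last three years". Section 6.1 admits men with up to 5 years of ED. Section 1.4 says of the 20-man pilot: "This significant result was consistent at 6-month follow up".

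The primary objective (section 3.1) and the null hypothesis (section 2.2) rest on IIEF-EF change from baseline within the treated groups. Both arms are active (section 7.1), and section 5.3 calls for an intention-to-treat analysis once a man is randomised.

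**The concern.** A change from baseline measures the effect of a course only if the baseline is free of an earlier course. The plan clears PDE5i for this purpose but makes no such provision for the study treatment itself when it was given outside research.

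Two kinds of pretreated men could enter. One still holds part of an earlier gain, so his baseline is raised and he has less room to improve. The other was treated before without success and may be unlikely to gain from a second course. Both pull an arm's mean change down. There is no sham arm against which this could cancel, and intention-to-treat keeps these men in the analysis. Because prior exposure is not a required data item, its influence might not be visible afterwards.

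**Working it through.** **1. Does any provision cover earlier routine-care shockwave?**

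- Other-study exclusion (6.2): research participation only, so routine care has no window at all.
- Investigator discretion over medications (6.2): drugs, not a device.
- Washout (7.3): PDE5i, 4 weeks.
- Ban on other ED therapy (7.3): from entry onward.
- IIEF-EF limit of 25 (6.1): removes only men whose carried-over response is near complete. If the pilot's post-treatment figures are read as mean 20.9 and SD 5.8 and taken as normal, the share above 25 is 1 − Φ((25 − 20.9)/5.8) = 1 − Φ(0.71), about 24%. About three quarters of such men would still qualify.

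None closes the gap.

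**2. Inputs for size.** The plan gives no figure for carry-over. Its only calculated figure is power (section 10.5: 0.852 with 40 per group). This reproduces with the Walters approximation at two-sided alpha 0.025, but it concerns response rates and plays no part here.

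Section 1.4 gives two gains:

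- Pilot, uncontrolled, at 1 month ("20.9 5.8 vs 13.5 4.1"): 20.9 − 13.5 = 7.4 points.
- Sham-controlled trial ("mean SEM 6.7 0.9 vs 3.0 1.4"): 6.7 − 3.0 = 3.7 points net.

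The pretreated share f is not in the documents and is assumed.

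**3. Effect on an arm's mean change.** Suppose untreated men gain c, and pretreated men hold their earlier gain throughout and add nothing. The arm's mean change is then (1 − f) × c, and the loss is f × c. The same loss follows for earlier non-responders who again gain nothing.

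| Assumed share f | Loss with c = 3.7 | Loss with c = 7.4 |
|---|---|---|
| 0% | 0 | 0 |
| 5% | 0.19 | 0.37 |
| 10% | 0.37 | 0.74 |
| 20% | 0.74 | 1.48 |

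For scale, the within-arm thresholds in section 2.1 are more than 2 points (mild ED) and more than 5 points (moderate ED). At f = 10% the loss is 0.37/2 to 0.74/2, or about 19% to 37% of the first, and 0.37/5 to 0.74/5, or about 7% to 15% of the second.

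**4. Effect on A versus B.** Under 1:1 randomisation the expected difference in pretreated share is zero. With 40 per arm and f = 10%, its SD is √(2 × 0.10 × 0.90/40) = 0.067. Multiplied by 3.7 and 7.4, this gives an SD of 0.25 to 0.50 points in the A-B difference. That is added noise with mean zero.

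**The case against.** The strongest reply is that the exposure is conjectural. Section 1.2 also describes the treatment as under evaluation and this device as a new type, and its remark on three years of use does not say where or whether outside research. The share could be zero, and then nothing follows. This stands, and it limits the weight of the point.

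The plan also describes its population as symptomatic ED patients (section 7.1), so admitting pretreated men could be a deliberate choice. Their history could come out at the screening interview or chart review. Both are possible, but the plan states no such choice, does not ask the question, and attaches no consequence to the answer.

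The likely direction, understating benefit, is conservative for a claim of improvement. That is fair, although a study reporting how much each schedule achieves still wants an undistorted figure.

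Three stronger readings are tempting and are not supported:

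- *A reader might infer that the 3-month window is simply too short against a 6-month effect.* For treatment inside a study this mostly fails. The natural reading counts from the end of participation, so a man in a study with 6 months of follow-up is excluded until about 6 + 3 = 9 months after treatment. At enrolment the window falls short of 6 months only if the earlier follow-up lasted under about 3 months or he left early. For routine care the window does not apply at all.
- *A reader might infer a false difference between the schedules.* Chance imbalance between randomised arms is noise covered by the test's error rate. The 2-point threshold in section 2.1 is a within-arm change and no yardstick for A against B.
- *A reader might infer a 7.4-point gain sustained to 6 months.* Section 1.4 gives 7.4 at 1 month, without controls, and no value at 6 months.

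**Conclusion.** The gap is real and worth closing: followed exactly, the plan admits men whose baseline may contain an earlier effect of the treatment under study. The consequence falls mainly on the within-arm IIEF-EF change and is probably an understatement. It is not certain to be one, since a man whose earlier response has worn off might respond again. The A-B contrast remains unbiased in expectation.

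The size cannot be established from the documents. The range of 0.37 to 0.74 points at a 10% share, and 0.74 to 1.48 at 20%, rests on three assumptions: the share itself, full retention of the earlier gain, and no further gain. It is pessimistic on the last two, though it does hold the carried-over gain constant; waning during follow-up would lower later scores. The 6 months in section 1.4 is a minimum duration set by the length of follow-up, not a measured end of effect. This is a cheap improvement to the design, not a flaw that invalidates the trial.

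**What to change.** Add to section 6.2 an exclusion for previous shockwave treatment of the penis or perineum, inside or outside a study. It should apply either ever or within a window that the sponsor justifies as longer than the 6 months in section 1.4. Add the matching question to the history and chart review in section 7.2.

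If a window is chosen, record prior exposure (whether and when) as a baseline variable and prespecify a sensitivity analysis of the IIEF-EF change without those men.

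The cost is one criterion, one history question and the few candidates already treated. The planned sample size and power are unchanged.

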6.3 Study Population

80 heterosexual males suffering from Vasculogenic ED.

7. STUDY DESIGN, CLINICAL, RADIOLOGICAL, LABORATORY AND SURGICAL EVALUATIONS

7.1 Study Design

This is a prospective, randomized, clinical study aimed to evaluate the safety and efficacy of the two treatment schedules on symptomatic ED patients. The patients are randomized in a 1:1 ratio into two active treatment groups. (Refer section 18)

7.2 Screening Evaluations and Procedures

The first visit of the patients will be for screening and medical evaluation. Patient's medical co-medication history will be collected and documented and a physical examination will be performed.

Previous month's blood test results will be reviewed including a general chemistry panel, a lipid profile, A1C and Testosterone levels during chart review.

Patients will sign an informed consent and will answer the IIEF-EF questionnaire to see if they fit the criteria for enrollment. In case they meet all inclusion criteria (and do not meet any exclusion criteria), they will be recruited to the study.

[figure not shown]
Patients who have been using PDE5-i in the last 4 weeks will report on their medicine type and dosage, and this data will be recorded in their files (reported prior to consent and gathered from chart review).

7.3 Pre-Treatment Procedures and Evaluations

Upon evaluating the inclusion/exclusion criteria, patients will be recruited to the study and randomized into one of the two groups in a 1:1 ratio (randomization will be performed by a computer software maintained by the Department of Urology). Patients randomized to the treatment groups will be instructed to stop any use of PDE5i for 4 weeks prior to first treatment session and refrain from using any other ED therapy option during the study. They will be instructed to undergo a PDE5i washout period of 4 weeks prior to treatment and to avoid using PDE5i or any other ED treatment during the entire study duration (shockwave treatment and follow-ups). After the washout period and before the first treatment session, patients will answer the IIEF-EF, SEP and EHS questionnaires for baseline evaluation.

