10.5 Statistical Analysis and Power calculation

The average and standard deviation of all relevant variables, including demographic and baseline characteristics, primary and secondary outcomes will be calculated.

IIEF-EF and EHS scores will be analyzed using ANOVA with repeated measures throughout the study, in order to compare the trends of groups A and B.

GAQ, SEP and success rates will be analyzed and compared between the groups according to Fisher's exact test in each of the endpoints. The statistical significance will be set at $P < 0.05$.

Demographic characteristics such as age and ED duration will be compared between groups A and B using student's test. Other demographic characteristics, such as medical background and risk factors will be compared between these groups using Fisher's exact test.

A sample of 80 men with failing scores on the IIEF SEP2 question will be randomized 1:1 into one of two arms (low intensity or high intensity treatment) using a permuted random block algorithm. We hypothesize that following placebo treatment between 0 and 5% of men will pass the SEP2 question and at least 35% of men treated at either intensity level will pass. We have two co-primary

endpoints, the percentage of men passing after low intensity and high intensity relative to placebo, which will be assessed by two independent Fisher’s exact tests. Each of these tests will be conducted with a 0.025 alpha error level to allow for a 0.05 experiment wide type I error rate. Power calculations done in SAS 9.4 suggest that with 40 men randomized into each group we will have at least 85% power to detect the difference between a 5% and 35% response rate. So long as our non-compliance/drop-out rate remains above 10% will will have at least 80% power (see Figure 1).

Computed N per Group			
Index	Nominal Power	Actual Power	N per Group
1	0.80	0.813	37
2	0.85	0.852	40
3	0.90	0.900	45

Figure 1. Sample size needed for 80% 85% and 90% nominal power for a Fisher’s exact test with alpha = 0.025 (using an exact conditional distribution with the Walters normal approximation method).

10.6 Randomization:

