80 patients will be randomized 1:1 to treatment groups with 40 patients each. An online based randomization tool called randomized.org will be used. This will be prepared beforehand, with treatment option printed on the paper and then sealed in an envelope (80 envelopes). Each would have Patients ID number printed out side and randomization information inside. This would be opened after a patient has signed the informed consent and is ready to receive treatment. The PI nor the study coordinator will not have the knowledge of patient’s treatment group beforehand.

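### Sections 7.3 and 10.6 place randomisation on opposite sides of the 4-week washout and name different tools; under the 7.3 order, men lost in washout enter the ITT set without a post-washout baseline

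*Combined protocol and SAP*

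**What the plan says.** Section 7.3 gives a sequence. First, once the entry criteria have been checked, "patients will be recruited to the study and randomized into one of the two groups in a 1:1 ratio". The tool is software maintained by the Department of Urology. Next comes the washout, addressed to men who already have an allocation: "Patients randomized to the treatment groups will be instructed to stop any use of PDE5i for 4 weeks prior to first treatment session". Baseline is last: "After the washout period and before the first treatment session, patients will answer the IIEF-EF, SEP and EHS questionnaires for baseline evaluation".

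Section 10.6 describes another process. Assignments come from an online tool, are printed beforehand and are sealed in 80 numbered envelopes. Of the envelope it says: "This would be opened after a patient has signed the informed consent and is ready to receive treatment". It adds: "The PI nor the study coordinator will not have the knowledge of patient’s treatment group beforehand". It does not say when the patient learns his arm relative to the questionnaires.

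Section 5.3 ties the analysis set to randomisation: whatever the reason for withdrawal, "once a patient has been randomized to an arm, an intention to treat analysis will be performed".

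The study calendar (section 17) lists recruitment and randomisation at Visit 2, Pre-Treatment, without dating that visit against the washout. It marks the questionnaires at Visit 1 and at the three follow-ups only.

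**The concern.** Site staff cannot follow both sections. Under 7.3 a man is allocated about four weeks before his first session; under 10.6 he is allocated when he is about to start. Two things depend on which is followed.

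The first is the analysis set. The primary objective (section 3.1) is change in IIEF-EF from baseline. A man allocated under 7.3 who leaves during washout counts under the rule in 5.3, but he has no post-washout baseline, no treatment and no follow-up score. Section 10.5 gives no rule for missing data.

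The second is how baseline is measured. IIEF-EF is self-reported, no patient blinding is described, and the two visit schedules are plainly different. If allocation precedes baseline, a man may know his arm when he answers, and that answer enters every one of his change scores.

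**Working it through.** **1. The two orders side by side**

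| Step | Section 7.3 | Section 10.6 |
|---|---|---|
| Consent and eligibility | before randomisation | consent before the envelope is opened |
| Allocation | at eligibility | when ready for treatment |
| 4-week washout | after allocation | before allocation, since readiness for treatment presupposes it |
| Post-washout questionnaires | after allocation | not placed relative to the envelope |
| Tool | department software | online tool, sealed envelopes |

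The calendar does not break the tie. An undated Visit 2 could lie before or after washout, and the baseline assessment that 7.3 requires after washout has no mark in any column.

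Section 10.5 is not part of the conflict. It says the men will be randomised "using a permuted random block algorithm". That describes how a list is generated, and a blocked list can be produced by either tool and placed in envelopes.

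**2. What a man lost in washout has on record under 7.3**

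He has a screening IIEF-EF (section 7.2 and calendar Visit 1). Appendix I asks about the past four weeks, and 7.2 allows for men who used PDE5i in that period. So for some men the screening score describes function with the drug, whereas the 7.3 baseline is meant to describe function without it. The two are not interchangeable. The same four-week recall means that, under 7.3, a baseline taken as washout ends covers a period lying after randomisation.

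**3. How many men**

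Input from the plan: 40 per arm (section 10.6). The washout loss rate is not given; 5-15% is an assumption. Loss per arm = rate × 40.

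- 5%: 0.05 × 40 = 2 men
- 10%: 0.10 × 40 = 4 men
- 15%: 0.15 × 40 = 6 men

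Section 10.5 accepts roughly 10% non-compliance or drop-out. Its wording says the rate must stay above 10%; below is evidently meant. Ten per cent of 40 is 4 men per arm. Washout losses would use half of that at 5%, all of it at 10%, and exceed it by 2 men at 15%, before any session is given and before any later drop-out.

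**4. What allocating after washout costs in recruitment**

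Men who must start washout to allocate 80 = 80 / (1 − rate), rounded up.

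- 5%: 80 / 0.95 = 84.2, so 85
- 10%: 80 / 0.90 = 88.9, so 89
- 15%: 80 / 0.85 = 94.1, so 95

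If only 80 start washout, the number allocated is 80 × (1 − rate): 76, 72 or 68.

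**The case against.** The best defence is that 7.3 describes assignment to a list and 10.6 describes disclosure. Section 10.6 is the dedicated randomisation section, prepares its list in advance and keeps the arm from the investigator and coordinator until the envelope is opened. If that were the intention, no one would know his arm early. But 7.3 speaks of men already randomised being sent into washout, names a different tool, and nowhere refers to a concealed assignment. The documents do not offer this reading, and it would leave the tool conflict in place.

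Four stronger inferences are tempting and not supported:

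- *That men will report baseline knowing their arm.* Section 7.3 does not say they are told. Nor can a direction or size of bias be derived: both arms are active, and the totals are equal (5 × 720 = 6 × 600 = 3,600 shocks per treated region). It remains a possibility that the order leaves open.
- *That the ITT analysis fails.* Post-randomisation loss creates missing data that an ITT analysis has to handle. The screening IIEF-EF exists, although it is pre-washout. ITT is weakened, not made impossible.
- *That the loss can be read as a fall in the power stated in 10.5.* That calculation concerns a SEP2 pass rate, which needs no change score, and compares each arm with a placebo group that this two-arm active design lacks. It does not measure the harm of a missing IIEF-EF baseline.
- *That the permuted blocks in 10.5 contradict the other sections.* They are compatible with both.

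It is also fair to say that loss up to about 10% falls within the plan's stated allowance. The difficulty is that the same allowance must also cover drop-out over treatment and six months of follow-up.

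**Conclusion.** The inconsistency is real: 7.3 and 10.6 differ on when allocation happens and on which tool produces it, and the calendar settles neither. If 7.3 is followed, every man lost in washout is an ITT participant with no post-washout baseline. On the assumed 5-15% loss that is 2-6 of 40 per arm, or 4-12 of 80 overall; the documents supply no rate, so this is a range and not an estimate. Possible knowledge of the arm at baseline is a second, unquantified risk that rests on the absence of any described patient blinding. Both problems are avoidable by ordering the steps, so the plan should be corrected, but neither by itself invalidates the comparison of the two schedules.

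**What to change.** State one order, identically in 7.3, 10.6 and the calendar: consent, eligibility, washout, post-washout baseline questionnaires, then opening of the allocation immediately before the first session. The place of the questionnaires needs its own wording, because being ready for treatment does not by itself mean they have been completed. Add the post-washout assessment to the calendar and date Visit 2 against the washout. Name one allocation source: the permuted-block list of 10.5, placed in the sealed envelopes of 10.6, with the competing tool removed.

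The costs are modest but not only editorial. Sessions can be booked only once a man is ready to start and his schedule is known. Washout losses do not disappear; they move ahead of allocation. Sections 4.1 and 10.4 fix accrual at 80, so the plan must say whether 80 counts men starting washout or men allocated. To allocate 80, about 85-95 would have to start at 5-15% loss; otherwise fewer than 80 are allocated and the plan should state that.
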